message understanding and appeal. This process will lead to the elimination of some SMS messages and to improvements in their wording. Validation recruitment will take place in urban and rural PHCs around the capital city of Jujuy.

Development of Automated Messaging system: We will develop an **Automated System (AS) to send SMS messages and e-mails based on data from SITAM**. This Automated system will send SMS messages and e-mails and will work in an asynchronous manner. E-mails sent to CHWs will not include personal information about women, but a secure link to registries of women to be viewed in SITAM. SMS messages and E-mails will comply with security procedures.

Intervention: cluster-randomized trial. Approximately 200 CHWs from the PHC system of Jujuy will be randomized into two groups: 1)

mHealth Intervention (MH) Group:

Women with positive self-collected tests will receive a **multi-component intervention** (Figure 1). HPV+ women will receive a weekly SMS message during the first month after self-collection result notifying them that test results are available, and they should go to the health center. In addition, CHWs will receive an e-mail and SMS message to visit those HPV+ women who, at 60 days since the HPV result have not attended triage. 2) ***Usual Care (UC) Group:*** Women with positive self-collected tests will receive usual care as described in Settings.

Hypothesis: Adherence to triage

will be higher in the MH intervention group compared to women receiving UC. Following the HBM,⁵⁶⁻⁵⁷ we assume that women are more likely to undertake a health behaviour (attend health center and complete triage) depending on the perceived severity, perceived threat of the disease, and perceived benefits of the recommended actions, concepts that account for the readiness to action. In addition, specific cues to action will activate that readiness and stimulate behavior. Using the HBM in this study is particularly appropriate because in the proposed intervention, the SMS messages serve as a cue to action, which will increase adherence (Figure 2). Also, the CHW visit to HPV+ women who have not responded to SMS reminders will be an additional cue to action, as well as an opportunity to provide counseling and support which will change women's perceived benefits and barriers of screening as well as perceived threat of cervical cancer.

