Outcomes: Primary outcome: **The percentage of women with triage smears at 120 days after HPV results are registered in SITAM.** This will allow measurement of the overall effect of the multi-component intervention including two periods: a) the 60 day period between the Test results and the SMS message and e-mail sent to CHWs (days 1-59); and b) the 60 day period between the SMS message and e-mail sent to CHWs and triage measurement (days 60-120). **Secondary outcome:**

[figure not shown]

Figure 1. The multi-component mHealth Intervention

[figure not shown]

Figure 2. Health Belief Model, adapted from Janz and Becker 1984⁵⁷

The percentage of women with triage smears at 60 days after Test Results, when the first SMS message is sent (days 1-59). This outcome will allow us to measure the individual effect of the SMS messages sent to women (before CHWs receive prompts to contact non-compliant HPV+ women).

[figure not shown]
Participant inclusion criteria: Women aged 30+ that have performed HPV self-collection offered by CHWs during routine home visits. Participants must be competent to understand the consent form, able to communicate with study staff, and provide a working mobile phone number capable of receiving calls and SMS messages.

Study procedures. CHWs from both groups will identify eligible women and invite them to participate in the study during their routine home visits. Once women have performed HPV-self collection, CHWs will screen for eligibility criteria, including use of mobile phones. CHWs will ask women whether they would provide a working mobile phone number capable of receiving calls and SMS messages. Those women who would provide such telephone number will be explained the study objectives and will be invited to participate in the study. Women accepting to participate will be asked to provide the telephone number. Based on a mHealth study in Northern Argentina among women with Chagas disease,³⁵ and a mHealth study in Buenos Aires among poor population with high blood pressure,⁶⁰ we expect approximately 85% of women will provide a telephone number; with 70% providing their own personal mobile phone.

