Randomization and sample size calculations: All CHWs (clusters) (approximately 700) of the Jujuy province offer self-collection and will be eligible to participate in the study. After classifying them into four groups according to gender and urban/rural setting, a stratified sample of 240 CHWs will be randomly selected with allocation proportional to strata. Selected CHWs will be invited to participate in the study following the order defined by the random list until 200 are enrolled. Enrolled CHWs will be randomly allocated to the MH or the UC group (3:2 ratio). The statistician will produce computer-generated random number lists for the CHW selection and the intervention allocation. Allocation concealment is guaranteed because all CHW will be assigned to the trial arms at the same time. Blinding of intervention and outcome assessments is not feasible due to the characteristics of the study. The number of CHWs was defined based on pragmatic considerations. From our experience¹⁴, this is a feasible number of CHWs that can be enrolled in the trial and trained in programmatic, routine conditions. We decided to allocate a larger number of CHWs to the MH group to be able to detect changes in the time series trend associated with the second component of the intervention

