(see Analysis Plan below). In addition, a larger number of CHWs in the intervention group will benefit the assessment of the implementation outcomes. Based on PHC records and previous experience¹⁴ we estimate that each CHW will enroll an average of 20 eligible women in a 10-month period. We assumed an attrition rate of 20% due to problems with mobile phones (i.e. non-identified number, unpaid phone bill, lack of signal, etc.), SMS messages not delivered and/or other issues. Under a 13% prevalence of HPV+ in this population,¹¹ we estimate that each CWH will contribute with an average of 2 HPV+ women. **Primary outcome:** The target sample size (120 CHWs in the MH group and 80 CHWs in the UC group, each one providing 2 HPV+ women) will have 97% power to detect a 20% triage difference between the two groups when the control group has a 30% triage in a 120-days period (two-sided test, alpha=0.05). Correlation induced by the CHWs was included in power calculations assuming an intra-class correlation coefficient of 0.10. **Secondary outcome:** Under the same assumptions, the proposed sample size will have 90% power to detect a difference of 10% in triage between groups when the control group has a 15% triage by day 60.

A specifically built database will be used (RCT database), combining information from the Trial Form, the AS Monitoring Registry, and SITAM, the national screening information system.⁵² The Trial Form will register information about the randomization group, agreement to participate in the study, women's socio-demographic data, and tasks performed by the CHWs (contact after reminder and reasons of no contact). Data on HPV testing, triage, diagnosis and treatment will be uploaded importing data from SITAM, linking the records through each woman's national identification number. The AS Monitoring Registry will include data from the Automated System regarding receipt of confirmatory SMS messages and e-mails, and valid phone numbers and e-mails. Data entry will be done through specific software that will include range and inter-item consistency checks. Data will be stored in files compatible for analysis with statistical packages (Stata).

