Potential problems and limitations: One of the potential limitations of randomization of CHWs is the **risk for contamination** due to CHWs assigned to different study groups, but working in neighboring areas, which could activate CHWs and women in the UC group. However, our prior work using CHW cluster randomization¹⁴ suggests that this risk is low and the effect of contamination is minimal. If such effect occurs, we expect them to be moderate because meaningful improvements in adherence to triage require a systematic effort to address problems related to follow-up adherence which are unlikely to occur in the absence of a specific intervention. Also, **it is not possible to blind CHWs (clusters) or women in this study.** However, laboratory personnel processing the HPV-test and personnel entering data in SITAM, the national screening information system, will be blind. Moreover, the assessment of primary and secondary outcomes will be objective, as data on triage is extracted from SITAM. Nevertheless we will compare demographics characteristics and screening history of women enrolled in the two study groups and will control in the analysis for any variable showing unbalance between study groups. Other problems that might affect the RCT are those related to **poor cell phone network coverage or reception or gaps in service due to unpaid telephone bills.** However, the sample size calculations accounted for this type of attrition, as described above. Finally, **if women do not confirm their identity within one week of initial SMS**

message reception, it will affect the delivery of the intervention (number of SMS messages the woman will receive). To minimize this potential problem, CHWs will emphasize the importance and ease of confirming identity as soon as possible, ideally within 24 hours, not exceeding 7 days.

We **evaluated and ruled out alternative designs** such as having a three group trial (comparing SMS messages to women vs. SMS messages to women + SMS message and e-mail to CHWs vs. UC) because the main aim of the trial is to assess the effect of the multi-component intervention, not each component separately. In addition, such a trial should include a larger number of CHWs, which would attempt against feasibility of a study that will take place in a real-world, programmatic context. Instead, we propose a time series approach to explore the differential impact of each component of the intervention.

Safety and monitoring

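### The 90% power stated for the day-60 secondary outcome does not follow from the plan's own inputs: 15% versus 25% gives about 64%

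*Combined protocol and SAP*

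**What the plan says.** The power statements are in section c (Approach), Specific Aim 1, under Randomization and sample size calculations. The sample is "120 CHWs in the MH group and 80 CHWs in the UC group, each one providing 2 HPV+ women", the test is two-sided at 0.05, and clustering is allowed for by "assuming an intra-class correlation coefficient of 0.10". For the primary outcome (triage at 120 days) the plan gives 97% power for a 20-point difference from a 30% control rate.

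For the secondary outcome it carries the same assumptions over and states that "the proposed sample size will have 90% power to detect a difference of 10% in triage between groups". The control rate assumed for this is 15%. The Hypothesis paragraph sets the direction: adherence "will be higher in the MH intervention group compared to women receiving UC". The comparison is therefore 25% (MH) against 15% (UC). The 25% is not printed; it is the stated control rate plus the stated difference.

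Under Outcomes, the day-60 measure has a specific purpose: "This outcome will allow us to measure the individual effect of the SMS messages sent to women", before the CHWs are prompted.

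**The concern.** The two power statements do not sit easily together. The sample and alpha are the same, but the second difference is half the size of the first. The lower base rate reduces the variance, though not by enough to make up for this: power should fall well below 97%, and a drop to only 90% looks too small.

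What is at stake is the reading of a null day-60 result. Under Potential problems and limitations the plan rejects a three-group trial and says instead that "we propose a time series approach to explore the differential impact of each component of the intervention", but it gives no power for that analysis. Day 60 is thus the only randomised comparison aimed at the SMS messages for which power is stated. A reader who trusts the 90% could take a non-significant result as good evidence that the messages alone do not achieve a 10-point gain.

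**Working it through.** **Inputs, all from Randomization and sample size calculations**

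- MH: 120 × 2 = 240 women. UC: 80 × 2 = 160 women.
- Design effect: 1 + (2 − 1) × 0.10 = 1.10.
- Effective sizes: 240/1.10 = 218.2 and 160/1.10 = 145.5.
- Two-sided alpha 0.05, z = 1.96.
- The 20% attrition is already in the 2 women per CHW: 20 × 0.80 × 0.13 = 2.08.

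**Formulas**, with d the difference and p̄ the weighted mean rate:

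- SE₀ = √[p̄(1 − p̄)(1/218.2 + 1/145.5)]
- SE₁ = √[p₁(1 − p₁)/218.2 + p₀(1 − p₀)/145.5]
- Pooled: power = Φ[(d − 1.96·SE₀)/SE₁]
- Unpooled: power = Φ[d/SE₁ − 1.96]
- Arcsine: power = Φ[h/√(1/218.2 + 1/145.5) − 1.96], with h = 2·arcsin√p₁ − 2·arcsin√p₀

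**Step 1. Reproduce the primary figure (50% vs 30%).** p̄ = 0.42, SE₀ = 0.0528, SE₁ = 0.0509. Pooled: Φ[(0.20 − 1.96 × 0.0528)/0.0509] = Φ(1.90) = 97.1%. Arcsine gives 97.0% and unpooled 97.6%. The stated 97% is reproduced.

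**Step 2. Same method, day 60 (25% vs 15%).** p̄ = 0.21, SE₀ = 0.0436, SE₁ = 0.0417.

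- Pooled: Φ[(0.10 − 1.96 × 0.0436)/0.0417] = Φ(0.35) = 63.7%.
- Arcsine: h = 0.2518, Φ(0.39) = 65.3%.
- Unpooled: Φ(0.44) = 67.0%.

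A simulation of clustered binary data (beta-binomial, intra-class correlation 0.10, cluster-robust logit test, 40,000 runs) gave 63.5%. The same simulation gave 96.9% for the primary outcome and 5.1% rejections when both arms were at 15%.

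**Step 3. Can another reading reach 90%?**

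| Change to the stated inputs | Pooled | Arcsine | Unpooled |
|---|---|---|---|
| 25% vs 15%, no clustering | 67.9% | 69.4% | 71.1% |
| 25% vs 15%, no attrition (2.6 per CHW, design effect 1.16) | 73.0% | 74.3% | 76.0% |
| 25% vs 15%, one-sided and no clustering | 78.7% | 79.5% | 80.9% |
| 25% vs 15%, one-sided, no clustering, no attrition | 87.5% | 87.9% | 89.0% |
| MH 15%, UC 5% | 87.2% | 89.6% | 91.2% |
| MH 5%, UC 15% | 88.6% | 89.6% | 85.6% |
| MH 30%, UC 15% | 92.0% | 92.5% | 93.8% |

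Reading the 10% as a relative increase (15% to 16.5%) gives about 6%. Only a different pair of rates brings the result to 90%. Pairing 15% with 5% contradicts either the stated control rate or the hypothesised direction, and 30% vs 15% contradicts the stated difference.

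**Step 4. What the sample can detect from a 15% control rate.** 90% power is reached at 14.4 points (pooled), 14.2 (arcsine) or 13.8 (unpooled); 80% power at 12.3, 12.1 or 11.8 points. If 25% vs 15% is observed, the expected 95% CI half-width is 1.96 × √[1.10 × (0.25 × 0.75/240 + 0.15 × 0.85/160)] = 8.2 points.

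**The case against.** The case against has four parts.

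- **The consequence is small.** This is one secondary outcome, and the 90% did not set the sample size: "The number of CHWs was defined based on pragmatic considerations". The plan also says that its main aim is the combined intervention. This stands, and it limits the point to how day 60 is read. It does not make the figure right, and the Outcomes paragraph gives day 60 a real job.
- **The attrition may not be lost outcome data.** It is attributed to phone and message-delivery problems, while outcomes come from SITAM and the analysis is by intention to treat. Such women could still be counted. Power would then be 73% to 76%, and the miss rate nearer one in four. This is a fair point about what the trial may achieve. However, the plan states its power for 2 women per CHW, and 76% is still far from 90%.
- **Relaxing everything together comes close.** A one-sided test with no clustering and no attrition reaches 87.5% to 89.0%. That is still short of 90%, and it breaks three stated assumptions.
- **The 25% is inferred.** This is true, but it follows from the stated direction. Reading the primary difference in the same way, as control plus 20 points, reproduces the 97%.

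The documents cannot show where the 90% came from. A calculation of 15% against 5% is a possible source and no more than that. The error does not depend on it.

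**Conclusion.** The concern holds. Under the plan's stated assumptions, power for a 10-point day-60 difference from 15% is about 64% (63.7% to 67.0% across three standard formulas), which is 23 to 26 points below the stated 90%. The risk of missing such a difference is 33% to 36%, not 10%. The result rests on 2 HPV+ women per CHW, an intra-class correlation of 0.10, a two-sided 0.05 test, and MH triage of 25% against UC triage of 15%. The text does not show whether the power or one of the rates is the wrong entry; only the sponsor can say. The primary power statement, the randomisation and the primary analysis are not affected.

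**What to change.** Reconcile the day-60 rates with the stated power in the sample size section.

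- If 15% vs 25% is intended, the sentence could read: *With the assumptions used for the primary outcome, the sample gives about 64% power to detect 15% (UC) vs 25% (MH) triage by day 60; 90% power is reached for a difference of about 14 percentage points (15% vs about 29%).*
- If other rates were intended, correct the control rate or the difference so that they agree with 90%.

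In either case it would help to name the power formula and to report the day-60 result as an estimate with its 95% CI. Both are good practice, but the correction does not depend on them.

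The cost is one sentence. The number of CHWs was fixed on feasibility grounds, so enrolment and design stay as they are. The only drawback is that a stated figure may become less favourable.

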MH Group: CHWs will carefully explain participants the sequence of SMS messages to be received depending on the Test results, and how they should proceed after reception of the SMS messages. If the woman does not have a personal phone, she will be asked if she is willing to be contacted and receive the proposed SMS messages on a shared phone. CHWs will inform women about the nature and content of the SMS messages to be received. They will also explain that they might come back for a personal visit if they have not performed triage 60 days after the test results. Therefore, consent to participate also means women agreement to be contacted and receiving SMS messages, even if phones are shared by several family members.

Women with positive self-collected tests will receive a multi-component intervention (Figure 1). Upon registration in SITAM of the HPV result at the laboratory, they will receive a weekly SMS message for four weeks, notifying them that the test results are available, and they should go to the health center. Messages will be stopped if a Pap result is registered in SITAM.

Sixty days after the date of the Test result, CHWs will receive an e-mail and SMS message informing them that there are HPV+ women who have not had Pap triage (if this is the case). The e-mail will also contain a secure link to the list of HPV+ women to be visited, as explained above. CHWs will be asked to confirm receipt of the e-mail for monitoring project processes. CHWs will visit these HPV+ women within 15 days of being notified, for an in-person reminder and counseling about the importance of attending health centers and have triage performed. The script for this visit will be developed based on the results of the FGD using HBM concepts to address issues of perceived susceptibility, perceived severity, and benefits of triage. If possible, CHWs will also provide support to address barriers (e.g., connecting women with transport available in some municipalities). We will track CHW visit information on the Trial form, including visit attempts, date of visit and issues addressed during counseling. The subgroup of HPV+ women visited by CHWs are given 30 days to

get screened as we consider that they are probably women facing specific obstacles (i.e. lack of transportation) and might need additional time to solve them. This timeline is in agreement with programmatic organization of the cervical cancer prevention process.

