Analysis plan: All analysis will be conducted on an intention-to-treat (ITT) basis; the effect of the multi-component mHealth intervention on the primary outcome will be assessed using a generalized estimating equations approach. The model (logit link, and binomial distribution) will include trial group as fixed effect and CHWs as the clustering variable. Potential effect modification due to rural/urban location of the woman and CHW gender will be evaluated. Baseline socio-demographic characteristics of the women will be compared between groups using the same model with link and distribution selected depending on the variable. Factors showing clear unbalance between arms will be included in the model proposed above to adjust for potential confounding. The same approach will be used to estimate the intervention effect on the secondary outcome. Analyses will be conducted using STATA 14.0 or SAS v.9.4. The trial will follow the CONSORT extension for cluster randomized trials reporting guidelines.⁶³

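### Covariates for the primary GEE are picked from observed imbalance under two loosely worded rules; one list fixed in advance should replace them

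*Combined protocol and SAP*

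**What the plan says.** The Analysis plan fixes the core of the primary model: a logit-link binomial GEE that "will include trial group as fixed effect and CHWs as the clustering variable". It then makes further covariates conditional on the data. "Baseline socio-demographic characteristics of the women will be compared between groups using the same model", and "Factors showing clear unbalance between arms will be included in the model proposed above to adjust for potential confounding". The same approach applies to the secondary outcome. Rural/urban location and CHW gender are named for effect modification only.

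Potential problems and limitations returns to the subject after conceding that "it is not possible to blind CHWs (clusters) or women in this study". There, "we will compare demographics characteristics and screening history of women enrolled in the two study groups", and the team "will control in the analysis for any variable showing unbalance between study groups".

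On recruitment, Randomization and sample size calculations has all CHWs assigned to arms at one time. Under Study procedures, "CHWs from both groups will identify eligible women and invite them to participate in the study during their routine home visits". In the mHealth (MH) arm the woman is told about the messages and a possible home visit, and "consent to participate also means women agreement to be contacted and receiving SMS messages".

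The same randomization section forms four strata (CHW gender by urban/rural setting) for sampling CHWs. It does not say whether the 3:2 allocation is made within them.

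**The concern.** The two rules differ in three ways. One needs the imbalance to be clear; the other acts on any imbalance. One looks at socio-demographics; the other adds screening history. One refers to the women without saying which set; the other refers to enrolled women, about 4,000, whereas the outcome model covers about 400 HPV+ women. Neither gives a threshold or a closed list of variables. An adjusted logistic odds ratio is conditional on its covariates, so what the primary estimate measures is also settled late.

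The practical risk is recruitment bias. CHWs know their arm when they invite women, and consent means something different in each arm, so the women enrolled may differ by arm. Concealed allocation of CHWs does not prevent this. A triggered rule corrects such a shift only when a test happens to detect it.

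**Working it through.** **1. The plan's power.** Inputs from Randomization and sample size calculations: 120 and 80 CHWs, 2 HPV+ women each, 30% v 50%, ICC 0.10, two-sided alpha 0.05.
- Design effect = 1 + (2 − 1) × 0.10 = 1.10. Effective sizes: 160/1.10 = 145.5 (usual care, UC) and 240/1.10 = 218.2 (MH).
- Pooled rate = (160 × 0.30 + 240 × 0.50)/400 = 0.42.
- Null SE = √[0.42 × 0.58 × (1/145.5 + 1/218.2)] = 0.0528. Alternative SE = √(0.21/145.5 + 0.25/218.2) = 0.0509.
- z = (0.20 − 1.96 × 0.0528)/0.0509 = 1.895, so power is 97.1%. The stated 97% reproduces. The calculation has no covariates, so this point does not touch it.
- Planned effect on the model's scale: ln[(0.5/0.5)/(0.3/0.7)] = 0.85.

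**2. How often a shift would be flagged.** Assumptions: screening history 50% in UC, 5 or 10 points higher in MH, test at p<0.05. The plan gives none of these.
- In 240 v 160 HPV+ women at 10 points: SE = √(0.60 × 0.40/240 + 0.25/160) = 0.0506, z = 1.98, flagged in 51%. With design effect 1.10, 47%. At 5 points, 16-17%.
- In 2,400 v 1,600 enrolled women (200 CHWs × 20): at 10 points, over 99% with design effect 1, and 96% with design effect 1 + 19 × 0.10 = 2.9. At 5 points, 87% and 45%.

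**3. Bias if a shift is left alone.** Assume no treatment effect, 30% triage in UC, and an odds ratio of 1.8 for screening history.
- Triage is 23.9% in the unscreened and 36.1% in the screened (mean 30%). At a 10-point shift the MH rate is 0.4 × 23.9% + 0.6 × 36.1% = 31.2%, and logit(0.312) − logit(0.300) = 0.06.
- With odds ratio 2.5 (20.6% and 39.4%) the result is 0.09.
- A simulation with further covariates and clustering gives 0.05-0.08 at 10 points and 0.03-0.05 at 5 points.

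**4. Bias under each approach.** Simulation of 8,000 trials per scenario, with an independence-working GEE and cluster-robust SE. Covariate prevalences and effects are assumed. The triggered rule includes screening history and uses p<0.05. Mean log-odds ratio, true value 0:

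| Shift | Triggered, tested in 400 HPV+ women | Triggered, tested in 4,000 enrolled women | Fixed list |
|---|---|---|---|
| 5 points | 0.02-0.03 | 0.00-0.02 | 0.00-0.01 |
| 10 points | 0.02-0.03 | 0.00-0.01 | 0.00-0.01 |

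The Monte Carlo SE of each mean is about 0.003. At 10 points, false significance favouring MH (nominal 2.5%) is 2.8-3.4%, 2.4-2.9% and 2.5-3.0% respectively.

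**5. No recruitment shift.** Two-sided type I error is 4.8-5.2% unadjusted, 4.7-5.2% under the triggered rules and 4.9-5.4% with the fixed list. Power at 30% v 50% is 96.8-97.1%, 96.7-97.1% and 96.9-98.0%.

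**The case against.** The strongest reply is that the two passages belong to one plan and do not exclude each other. The Analysis plan does not say that only socio-demographic factors may enter, and the limitations paragraph adds screening history as a safeguard against lack of blinding. This stands. A reader might infer that screening history would never be adjusted for, leaving a bias of 0.05-0.08 and false significance of 4.1-5.4% at a 10-point shift. Those figures describe a plan with the limitations paragraph ignored, and the documents do not support that reading.

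A reader might also infer that the two rules would often give different models. That requires one rule to be tested in HPV+ women and the other in enrolled women, and the Analysis plan does not say which women it means. Inflated type I error and lost power are likewise not supported (steps 1 and 5).

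The plan has another safeguard: the UC care group section collects age, insurance, education and refusal reason from women who decline, so enrolled and non-enrolled women can be compared. It is a direct check on selective enrolment, though it omits screening history.

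The fixed list also moves the estimate. It lies more than 5% from the unadjusted odds ratio in 15-16%, 46% and 69-70% of simulated trials (covariates not, moderately or strongly prognostic). A pre-declared unadjusted model would end the ambiguity too, but it would leave a recruitment shift uncorrected. What survives is that adjustment still depends on an undefined flag raised after the data are seen.

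**Conclusion.** The point holds as a cheap improvement with a small numerical effect. The covariate set of the primary GEE is data-driven, has no threshold, and is described in two places in different words. Under the assumed 5-10 point shift and odds ratio of 1.8-2.5, the triggered rule leaves a log-odds bias of about 0.00-0.03, against 0.00-0.01 with a fixed list. Even 0.03 is under 4% of the planned 0.85 (0.03/0.85 = 3.5%). The shift, the prevalence, the covariate effects and the p<0.05 trigger are all assumptions. That the model is left open until the data are seen, and that unblinded CHWs recruit after allocation, rests on the text alone.

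Silence on stratified allocation is a missing detail. A reader might take it to mean that the allocation is unstratified, but the text neither states nor excludes that.

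**What to change.** Replace both rules with one, for the primary and secondary outcomes. The GEE includes trial group, CHW gender, CHW urban/rural setting, and the woman's age, education, health insurance and screening history (any event in SITAM, the screening information system, before the enrolment test), irrespective of balance. The sponsor chooses the codings and the handling of missing covariates, writes them down before data are seen, and keeps all intention-to-treat women in the model.

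Label the adjusted odds ratio as conditional and report the unadjusted GEE as a sensitivity analysis. Keep the baseline comparison, together with the enrolled v non-enrolled comparison, only as a check for recruitment bias. In the database description, state that SITAM records from before enrolment are imported. The text lists the types of SITAM data but not the period, and the Trial form description does not name screening history. As a minor clarification, say whether the 3:2 allocation is made within the four sampling strata.

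The cost is a few sentences and a few degrees of freedom out of 200 clusters. SITAM covers only the public sector, so screening elsewhere is missed in both arms. Because the odds ratio is conditional, its mean log value rises to 0.87-0.94 across the simulated scenarios, against 0.85-0.86 without the list. Sample size and stated power do not change.
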